17.2 Data Collection

17.2.1 Baseline

Baseline assessments may be completed in the outpatient clinic, pre-operative assessment clinic, designated research clinics or on the ward during admission for surgery. Patient demographics will be captured at baseline and in part used to describe the population included and assessed to evaluate equality, diversity, and inclusion of participants taking part. The KOOS, EuroQol EQ-5D-5L, emotional functioning questions taken from KQoL-26 and Modified Tegner, collated as a Baseline Questionnaire, will be collected prior to randomisation. Ideally, the Patient-Reported Outcome Measures (PROMs) will be completed in clinic but, if the participant requests to complete the PROMs outside of clinic (either on paper or electronically), this is permissible, but they will have to return the completed form to site staff prior to randomisation.

17.2.2 Follow-up assessments/subsequent visits

Follow up for study purposes will be by patient self-reported questionnaire completed using a web-based data collection system (REDCap). The option of being able to fill out the follow-up questionnaires in a hard copy and returning via post will also be available. The questionnaires will contain the following outcome measures: KOOS, EQ-5D-5L/VAS, emotional functioning questions taken from KQoL-26, Tegner, and will be sent out at 6-, 12- and 24-months post randomisation to all participants. Patient satisfaction and return to sport outcome measures will be added to the 12- and 24-month questionnaires. The questionnaires will also ask participants if they have returned to see a health care professional or been admitted to hospital in relation to complications with their study knee, and time away from paid employment and education. The central CTU study team will follow up any complications reported by participants with the research team at the participant's local hospital. Further details about the event will be collected and recorded on a complications form.

A final readmission checklist will be undertaken by the Research staff on hospital records at 24 months post randomisation to ensure that all complications data is collected from all participants (i.e. those who had not returned a questionnaire). Data from any readmission events identified will be recorded in a "Complications" CRF. The physiotherapy case report form (PCRF) will be used to record the number of post-operative rehabilitation physiotherapy sessions attended, and the date of discharge from physiotherapy. If a participant attends community-based physiotherapy, the number of sessions attended will be reported via the patient questionnaires.

Patients will also be asked to complete a pain numerical rating scale to report their post operative pain at 3- and 6-weeks post randomisation. A link to complete the score online will be sent by either SMS, email or post. Contact preferences will be recorded in REDCap after consent.

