17.1 Overview

Table 1 shows scheduled assessments for the study.

Table 1: Schedule of assessments

Assessments	Screening	Baseline	Day of Surgery	3- & 6-weeks post randomisation	6 months post randomisation	12 months post randomisation	24 months post randomisation
Screening - Identification	*						
Screening - Eligibility	*						
Patient information given	*						
Consent		*					
Eligibility confirmation			*				
Randomisation			*				
Surgeon confidence in the ACL surgery performed (Surgery CRF)			*				
Demographics	*						
Post operative pain (pain NRS) via SMS message, email or post				*			
KOOS (Patient Questionnaire)		*			*	*	*
EuroQol-5D-5L / VAS (Patient questionnaire)		*			*	*	*
EuroQol-5D-5L / VAS Retrospective Baseline - Pre-injury (Patient		*					
questionnaire)							
Emotional functioning (Patient questionnaire)		*			*	*	*
Tegner (Patient questionnaire)					*	*	*
Modified Tegner (Patient questionnaire)		*					
Patient satisfaction (Patient questionnaire)						*	*
Time to return to sport (Patient questionnaire)						*	*
Physio attendance (completed once the pt has been discharged from						*	*
post-op physiotherapy, or at 24 months post-randomisation)							
Resource use /Health economics (Patient questionnaire)					*	*	*
Intervention related complications including re-operation (Patient					*	*	*
questionnaire -> Hospital records check -> Complications CRF)							
+ Intra-operative complications (Surgery CRF)+ Post-operative, pre-discharge complications (InPatient CRF)			*				
Intervention related complications including re-operation (Hospital							*
records check -> Complications CRF)							
Safety data collection			*		*	*	*
Objective evidence of graft/repair failure (defined on clinical assessment, imaging or operative assessment) (Hospital records check) (if required)			*		*	*	*

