21.2 Definitions

Table 3: Definitions of Adverse Events

An adverse event (AE)	Any untoward occurrence in a clinical study participant. Note: An AE can therefore be any unfavourable and unintended sign (including an abnormal laboratory finding, for example), symptom or disease temporarily associated with the study procedures, whether considered related to the procedures. For ACL STARR, AEs will only be collected if relevant to the knee, the surgery, the anaesthesia or the rehabilitation and will be captured as complication data. It will be recorded on a complication CRF.		
Related Adverse Event	An event that resulted from administration of any of the research procedures		
Serious Adverse Event (SAE)	An AE that: • results in death • is life-threatening¹ • requires hospitalisation or prolongation of existing hospitalisation • results in persistent or significant disability or incapacity • is a congenital anomaly or birth defect; or • is otherwise considered medically significant by the Investigator²		
Unexpected Related Serious Adverse Event	A serious adverse event related to the study (i.e. resulted from administration of any of the research procedures) and is unexpected (not listed in the protocol as an expected occurrence).		

¹ participant was at risk of death at the time of the event; it does not refer to an event which hypothetically might have caused death if it were more severe

A distinction is drawn between serious and severe AEs. Severity is a measure of intensity whereas seriousness is defined using the criteria above. Hence, a severe AE need not necessarily be serious.

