21.3 Expected adverse events

The expected adverse events related to the procedures are outlined below, and will be collected as complication data on CRFs, separating intra-operative complications, post-operative pre-discharge complications, and post-discharge complications. All complications will be graded using a standard classification, 'The Clavien-Dindo Classification of Surgical Complications' (38). Participants will be informed of the standard risks associated with the anaesthetic and the surgical procedure.

All ACL repair or reconstruction procedures whether primary surgery or revision carry a risk of
anaesthesia related problems which can include death, morbidity including wound infection,
bleeding intra and post operatively, pulmonary embolism (PE), deep vein thrombosis (DVT),
confirmed cerebrovascular accident (CVA), confirmed myocardial infarction (MI), and
complications secondary to existing comorbidity e.g. ischaemic heart disease, septicaemia, the
need for blood transfusion and revision operation.

² Medical events that may jeopardise the participant or may require an intervention to prevent one of the above characteristics/consequences.

- Specific complications following both ACL reconstruction and ACL repair procedures include:
 patella fracture, patella tendon avulsion, anterior knee pain, vascular injury and bleeding,
 femoral tunnel blowout, nerve damage (including numbness or weakness), complex regional
 pain syndrome, lack of extension/fixed flexion deformity, stiffness, infection, graft failure and
 continued instability, delayed wound healing, continued or worsened pain, fracture,
 compartment syndrome, swelling, additional contralateral graft harvest (reconstruction-only)
 and newly acquired meniscal pathology.
- Specific complications following rehabilitation include continued instability and subsequent newly acquired meniscal pathology causing pain. These complications may result in the need for further surgery.

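### The participant complication question covers only the study knee and is first asked at 6 months, so post-discharge non-knee events without a visible readmission may be recorded late or not at all

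*Protocol*

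**What the plan says.** Section 21.2 (Table 3) sets the scope of collection: "AEs will only be collected if relevant to the knee, the surgery, the anaesthesia or the rehabilitation". Section 21.3 lists the expected events to be recorded as complication data, split into intra-operative, pre-discharge and post-discharge. Its general list includes "bleeding intra and post operatively, pulmonary embolism (PE), deep vein thrombosis (DVT") and, in the same sentence, wound infection, stroke, myocardial infarction and septicaemia.

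After discharge, the participant-facing trigger is described in Section 17.2.2. The questionnaire asks whether the participant has gone back to a health care professional or "been admitted to hospital in relation to complications with their study knee". The questionnaires "will be sent out at 6-, 12- and 24-months post randomisation to all participants". Table 1 (Section 17.1) shows the chain at those visits: patient questionnaire, then hospital records check, then Complications CRF.

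There is an earlier contact. Section 17.2.2 states: "Patients will also be asked to complete a pain numerical rating scale to report their post operative pain at 3- and 6-weeks post randomisation". Table 1 lists it as "Post operative pain (pain NRS) via SMS message, email or post". The 3- and 6-week column has no entry for complications or for safety data.

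Two other routes are stated alongside these. Table 1 has, on the day of surgery, "Intra-operative complications (Surgery CRF)+ Post-operative, pre-discharge complications (InPatient CRF"). Section 17.2.2 adds a backstop: "A final readmission checklist will be undertaken by the Research staff on hospital records at 24 months post randomisation".

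**The concern.** The question that starts post-discharge collection is narrower than the set of events the Protocol undertakes to collect. A participant treated for a clot or a cardiac event after the operation may not think of it as a complication of the study knee. If so, the questionnaire chain in Table 1 does not start for that event.

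Timing adds to this. Safety reporting begins at surgery (Section 21.1), but participants are first asked about complications at 6 months. Two scheduled contacts before then collect only a pain score. Minor early events, including knee events that fit the wording, therefore depend on recall over several months.

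At stake is the secondary comparison of complications. Section 8 gives the potential for fewer surgical complications as one reason to consider repair. Section 23.3.2 tabulates complications by type, frequency and arm, and Section 9.3 lists complication data among the cost-effectiveness inputs. The DSMC may recommend pausing or stopping on safety grounds (Section 23.6.1), so completeness and speed of collection matter to it too.

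**Working it through.** This is mainly a comparison of texts. No figure in the Protocol bears on complication capture, so there is none to reproduce.

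**1. Scope against question.** Section 21.2 covers four domains: knee, surgery, anaesthesia, rehabilitation. The Section 17.2.2 question covers one. Set against the events in Section 21.3:
- Infection of the operated knee's wound is inside the question. Only delay and recall apply.
- A deep vein thrombosis is ambiguous; some participants would link it to the knee and some would not.
- Pulmonary embolism, stroke, myocardial infarction and other anaesthetic or comorbidity-related events are outside the natural reading.

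**2. What each other route reaches.**
- Surgery and InPatient CRFs: events up to discharge. The synopsis describes day surgery, so this window is short.
- SAE reporting (Section 21.6): serious and related events, within 24 hours of the site becoming aware. It does not itself create awareness, and non-serious events fall outside it.
- Resource-use questionnaire (Section 24): treatment-related re-admissions, adverse events, primary care and outpatient contacts. This is wider than the knee, but also first asked at 6 months.
- 24-month check (Sections 17.2.2 and 21.5): a readmission checklist on hospital records, meant to cover all participants. What it records is readmission events. The text does not say that records of other hospitals are searched.

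**3. What is left.** A post-discharge, non-knee event with no readmission in the checked records, and unknown to the site, has only the 6-month-or-later resource-use items to bring it to light.

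**4. Delay.** Take 6 months as about 26 weeks. For an event in week 2 that the site does not learn of, the first question comes 26 − 2 = 24 weeks later. An item at the 3-week contact would ask 3 − 2 = 1 week later.

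**5. Scale, by assumption only.** With 107 per arm, one missed event changes an arm's rate by 1/107 = 0.93 percentage points. The Protocol gives neither event risks nor capture proportions. For assumed true risks, expected events = 214 × risk, and recorded events = that number × assumed capture of 50% to 90%:

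| Assumed risk | Expected in 214 | Recorded at 50% to 90% capture |
|---|---|---|
| 0.5% | 1.07 | 0.54 to 0.96 |
| 1% | 2.14 | 1.07 to 1.93 |
| 2% | 4.28 | 2.14 to 3.85 |
| 5% | 10.70 | 5.35 to 9.63 |

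The counts are small, so a few missed events could be visible in a descriptive table. The table does not show that any would be missed.

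**The case against.** The strongest reply is that the knee question is not the only net. Section 17.2.2 summarises the questionnaire, and the instrument itself is not shown. Section 9.3 names the Health Economics Questionnaire as a source for complications, and Section 24 says the patient questionnaires collect treatment-related adverse events and health care contacts. Pulmonary embolism, stroke, myocardial infarction and septicaemia would usually meet the seriousness definition in Section 21.2. Once a site knows of one and judges it related, reporting is due within 24 hours, whatever the questionnaire asks. An admission at the recruiting hospital should be found at 24 months. Routine clinic and physiotherapy contacts may also bring events to a site's notice. Complications are reported descriptively, both arms get the same questions, and participants are blinded. Nothing in the Protocol promises safety questions at 3 or 6 weeks.

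Most of this stands, and it limits the point. A reader might infer that the named systemic harms, and wound infection with them, are under-collected as a matter of fact. The documents do not support that: several routes reach these events, operated-knee wound infection fits the question, and no capture rate is given. Nor do they support an inference that any loss would favour one arm.

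The reply does not remove the mismatch between Sections 17.2.2 and 21.2. It also does not supply a prompt, broad route for events managed without a readmission. The resource-use items come no earlier than the knee question, and a readmission checklist cannot by itself deliver the full complication data that Section 17.2.2 expects of it.

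**Conclusion.** The point holds as an internal mismatch with a limited consequence. The described complication question is narrower than the Protocol's own adverse-event scope and expected-event list, and it is first put at 6 months. The events at risk of late or incomplete recording are those after discharge that leave no readmission in the checked records, typically a deep vein thrombosis managed as an outpatient, in primary care or at another hospital. For operated-knee wound infection the only issue is delay and recall.

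The size cannot be calculated from the documents; the table above rests wholly on assumed risks and capture. The conclusion also assumes that the questionnaire follows the description in Section 17.2.2 and that the 24-month check is confined to readmissions, as its name and Section 21.5 suggest. The primary outcome and the sample size of 214 are unaffected. Asking at 3 and 6 weeks is an improvement to the design; its absence contradicts nothing in the Protocol.

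**What to change.** 1. Reword the 6-, 12- and 24-month item so that it matches Section 21.2. Ask about any care or admission, at any hospital, for problems with the knee, the surgery, the anaesthetic or the rehabilitation, and mention blood clots explicitly. Amend the description in Section 17.2.2 to agree.
2. Add one yes/no complication item to the 3- and 6-week pain contact. A yes would follow the route already in place: the central CTU team asks the site, and the site completes the Complications CRF.
3. Mark complications and safety data collection in the 3- and 6-week column of Table 1.

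The cost is one reworded item, one added item on a message already sent, and a small amendment to the Protocol and participant questionnaires. The early message becomes slightly longer and sites will receive a few more queries.

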17.3 Study questionnaires

Participants will be emailed a link to complete their study questionnaires electronically where possible (participants will be asked at their baseline visit whether they wish to complete follow-up questionnaires electronically or on paper with postal return). Any links sent to a participant either by email or text to a questionnaire is unique to a participant and their timepoint/questionnaire in the study. Paper administered questionnaires may also be used if requested, where use of electronic

means is not possible or suitable. Where paper-based questionnaires are used, data will be entered into REDCap by the central CTU study team.

17.4 Communication with study participants by the CTU study team

Participants will be notified to complete study questionnaires by email, or where they have selected to receive postal questionnaires, these will be posted to the participant. Participants may be sent up to two reminder messages and/or where possible may be asked to complete questionnaires during a routine clinic visit. Participants that do not complete their study questionnaires, may be telephoned and/or texted to collect the data or request return of the questionnaire.

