15.2 Randomisation procedure

Initial eligibility / final eligibility will be confirmed at the point of randomisation. Participants will be randomised by the site research team using REDCap.

Participants will be randomised to one of the following arms:

Arm	Treatment (or Description)		
Arm 1 ACL Repair (intervention)	This group will have surgery to repair the ACL, with the		
	ligament being stitched back onto the bone.		
Arm 2 ACL Reconstruction (usual	This group will have surgery to reconstruct the ACL. This will		
care/comparator/control arm)	involve replacing the torn ACL with other tissue i.e.		
	hamstring to act as a replacement.		

Upon randomisation of a participant, the ACL STARR central CTU study team and a member of the site research team will be notified by an automated email. Full details of the randomisation procedure will be stored in the Randomisation and Blinding Plan in the confidential statistical section of the TMF.

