18 BLINDING AND CODE BREAKING

18.1 Blinding

Table 2 provides an overview of the blinding status of all individuals involved in the conduct and management of the study.

Table 2: Blinding status of those involved in study conduct and management.

Role in study	Blinding status	Additional information
Participants	Blinded	All participants will be blinded to treatment allocation.
		In-theatre randomisation precludes any potential for patients to be unmasked or biased from cues prior to the operation. Patients will have a blinded operation note within their hospital medical records with the detailed operation case report form kept within the study paperwork.
Site research staff including Principal Investigator (may need to be broken down further if different levels of blinding/unblinding with the team)	Not blinded: Surgeons Blinded: aftercare personnel (physiotherapy), patient follow	It is not possible to blind the surgeons as to the procedure that they perform, but aftercare personnel (physiotherapy), patient follow up and research staff will be blinded to allocated intervention. Patient notes will refer to 'ACL surgery' not the treatment allocation. CRFs accessed by research staff will also not contain the treatment allocation.
with the team,	up and research staff	Following randomisation, an email will be sent to the PI (unblinded for participants they randomise only) and/or member of the site research team performing the randomisation (as delegated) confirming treatment allocation.
Chief Investigator	Blinded for those at sites other than their own, except for any SAE causality assessment	It is not possible to blind the Chief Investigator as they may be the primary clinician for those participants recruited at their site, however they will be blinded to allocations for participants at other sites. In instances where serious adverse events are reported, the CI will become unblinded to complete the full causality assessment.

Data collection system programmer	Not blinded	The programmer is responsible for the management of the randomisation system and the REDCap data collection system and will have access to all unblinded datasets within both systems.	
ACL STARR Central CTU Study Team	Not blinded	Will not be blinded to the allocation. Serious Adverse Event reports will be handled by the central CTU study team.	

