18.2 Code break/ unblinding

The operating clinician and the central study team will not be blinded to the allocation, so no code break procedure for clinical care or safety reporting is needed. The central study team will discuss specifically with each site which techniques they will employ to ensure participant and staff blinding. In any case in which unblinding is needed, or in which it occurs accidentally, the study team will follow processes as per the OCTRU Standard Operating Procedures (SOPs).

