25.6 Data Recording and Record Keeping

The case report forms will be designed by members of the study management team which will include the Chief Investigator, study statistician(s) and study manager.

Data will, wherever possible, be collected in electronic format with direct entry into REDCap by site staff or participants. Electronic data collection has the major advantage of building "data logic" into forms, minimising missing data, data input errors and ensuring the completeness of consent and assent forms. REDCap (Research Electronic Data Capture) is a secure, web-based application designed to support data capture for research studies, providing 1) an intuitive interface for validated data entry; 2) audit trails for tracking data manipulation and export procedures; 3) automated export procedures for seamless data downloads to common statistical packages; and 4) procedures for importing data from external sources.

All data entered will be encrypted in transit between the client and server. All electronic patient-identifiable information, including electronic consent forms, will be held on a server located in an access-controlled server room at the University of Oxford.

The data collection system and server are backed up to a secure location on a regular basis. Details of the data collected, where it is stored and who has access to it along with a fair processing statement will be available for the participants within the study participant information sheet.

Direct access to source data/documents will be required for study-related monitoring and/or audit by the Sponsor, research team or NHS Trust or regulatory authorities as required.

Data captured during phone calls to participants or from paper-based study questionnaires returned to the central CTU study team will be entered into REDCap by suitably trained study team staff. Full details of this process will be recorded in the Data Management Plan. Identifiable data will only be

accessible by members of the research team with a demonstrated need (managed via access controls within the application) and only used to communicate with the participant e.g. sending follow-up reminders for online form completion or telephone follow-up).

Refer to Section 29.5 for details about retention of participant identifiable data.

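### Section 17.4 lets some 24-month KOOS-4 scores be taken by telephone, apparently by a central team that Table 2 lists as not blinded; the exposure is probably small and cheap to close

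*Protocol*

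**What the plan says.** Section 17.4 is headed "Communication with study participants by the CTU study team". After email or postal delivery, up to two reminders and possible completion at a routine clinic visit, it adds: "Participants that do not complete their study questionnaires, may be telephoned and/or texted to collect the data or request return of the questionnaire". Collecting the data and asking for the form back are given as alternatives, so the call is more than a reminder.

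Section 25.6 confirms that answers taken this way become study data: "Data captured during phone calls to participants or from paper-based study questionnaires returned to the central CTU study team will be entered into REDCap". It assigns this to suitably trained study team staff and leaves the details to the Data Management Plan. Section 17.2.2 puts the KOOS in the 6-, 12- and 24-month questionnaires, so the route reaches the primary outcome.

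On blinding, the central CTU study team's entry in Table 2 (Section 18.1) reads: "Will not be blinded to the allocation". Section 18.2 repeats it: "The operating clinician and the central study team will not be blinded to the allocation". Neither makes an exception for staff who telephone participants. The site research staff row of the same table says that "patient follow up and research staff will be blinded to allocated intervention", but that row does not cover the CTU. Under Section 15.2 the central team also hears of each randomisation by automated email.

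Section 9.2 gives the source of follow-up KOOS-4 as self-completion, on paper or straight into REDCap. Telephone is not listed.

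**The concern.** KOOS-4 at 24 months is a subjective score and the only primary outcome. The protocol takes real trouble to protect it: allocation is made in theatre, the operation note in the hospital record is blinded, and physiotherapists and site follow-up staff are blinded. A telephone interview by someone who knows the arm bypasses those safeguards. The caller may, without intending to, influence how an item is heard or how an answer is coded, or may let the allocation slip to a participant who is meant not to know it.

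The main analysis is complete case (Section 23.3), so a score taken by phone enters it like any other. The planned pattern-mixture analysis (Section 23.3.1) deals with scores that are missing, not with scores obtained by a different mode. The protocol does not provide for recording the mode, and without that record nobody could later say how many scores were affected or whether they differed.

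**Working it through.** **Step 1. The plan's own figure.** Inputs from Section 23.2: target difference 9 points, SD 20, two-sided 5%, 90% power, baseline correlation 0.37, 15% missing, 1:1 allocation.

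- Two-sample t test, non-central t: 105 per arm.
- Adjusted for baseline and inflated for missing data: 2 × 105 × (1 − 0.37²) / 0.85 = 210 × 0.8631 / 0.85 = 213.2. Rounded up per arm, this is 2 × 107 = **214**, as stated.
- Analysed: 214 × 0.85 = 181.9, about 91 per arm. Power is then 90.1% for 9 points and 82.3% for 8 points.

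The sample size reproduces, and nothing in this point changes it.

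**Step 2. Who could collect what, and knowing what.**

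| Question | Where | Answer |
|---|---|---|
| May answers be taken by phone? | 17.4, 25.6 | Yes, for non-completers |
| Does this include KOOS? | 17.2.2 | Yes, at 6, 12 and 24 months |
| Who calls? | 17.4 heading, 25.6 | CTU study team, by inference; the sentence in 17.4 is passive |
| Is that team blinded? | Table 2, 18.2 | No, with no exception stated |
| Is phone a listed source of KOOS-4? | 9.2 | No |
| Expected share by phone? | – | Not stated |

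**Step 3. Size of the exposure.** Let f be the share of analysed 24-month scores taken by phone, the same in both arms, and b the difference between arms in the shift that unblinded calling causes in those scores. Then

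bias in the treatment difference = f × b.

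The protocol gives neither f nor b; both are assumptions. One figure helps to place f. Section 23.2 reports 22% missing at 18 months in the earlier trial (ACL SNNAP) and plans for 15% here. If telephone collection alone closed that gap, it would supply 0.07 × 214 ≈ 15 scores, or 15 / 182 ≈ 8% of those analysed. That is an illustration only. Taking f as 7% to 10% and b as 3 to 5 points:

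- Low end: 0.07 × 3 = 0.21 points; 0.21 / 9 = 2.3% of the target.
- At 8%: 0.08 × 3 = 0.24 to 0.08 × 5 = 0.40 points.
- High end: 0.10 × 5 = 0.50 points; 0.50 / 9 = 5.6% of the target.

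**Step 4. Against the precision of the trial.** Residual SD = 20 × √(1 − 0.37²) = 18.6. SE of the difference = 18.6 × √(2/91) = 2.75 points. The high-end bias is 0.50 / 2.75 = 0.18 of a standard error and raises the two-sided type I error from 0.050 to about 0.054.

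**Step 5. Harsher assumptions.** With f = 10% and b = 10, the shift is 1.0 point and the type I error about 0.065. With f = 20% and b = 10, the figures are 2.0 points and about 0.112. The effect becomes material only if many scores come by phone and callers shift them strongly; nothing in the protocol suggests either.

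**The case against.** The strongest reply is that this is a disclosed choice with a weak mechanism. The trial is titled single blind and Table 2 openly lists the CTU as not blinded. The blinding of follow-up staff is promised in the site row only, so the table does not contradict itself. Telephone comes last and is optional. Part of the same route is by text, and under Section 17.3 a texted link leads to self-completion with no interviewer. The participant is blinded and answers fixed Likert items, so a bias between arms needs callers who know the arm and let it affect what they say or record. The alternative to a call is often a missing primary outcome, which carries its own bias in a complete-case analysis. Section 25.5 limits data access by role, and Section 25.6 defers the process to the Data Management Plan, which may well mask callers.

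Much of this stands, and it is why the size is put low. What does not stand is that the other documents settle the matter. Neither section says that callers are masked, and Table 2 and Section 18.2 state the opposite for the whole team.

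Two stronger readings are tempting. A reader might infer from Section 15.2, where "Upon randomisation of a participant, the ACL STARR central CTU study team and a member of the site research team will be notified" by automated email, that the email tells the CTU which arm was drawn. The section does not say so; Table 2 mentions confirmation of allocation only in an email to the site's principal investigator or the site member who randomises. A reader might also infer that a large part of the primary outcome will come by phone. No share is given, and the only anchor in the protocol leads to about 8%.

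**Conclusion.** The point holds as a limited one. The protocol, as written, permits some 24-month KOOS-4 scores to be taken verbally by staff listed as knowing the allocation, and it does so by a route that Section 9.2 does not list. Sections 9.2, 17.4, 18 and 25.6 need to be reconciled.

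The likely effect is small: about 0.2 to 0.5 points, or 2% to 6% of the 9-point target, and less than 0.2 of a standard error. This rests on an assumed phone share of 7% to 10%, equal in both arms, an assumed 3 to 5 point differential, and the inference that the CTU team makes the calls. The sample size is untouched. The documents do not support saying that the primary outcome is biased or that blinding has failed. They show an avoidable exposure that, without a record of mode, could not be measured afterwards.

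**What to change.** Keep the telephone route, since it rescues primary outcome data, and change who uses it and how it is recorded.

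- In 17.4, Table 2, 18.2 and 25.6, state that verbal collection of KOOS and other patient-reported outcomes is done only by existing staff whose REDCap role hides the allocation and the surgery data. If the randomisation email shows the arm, these staff should receive a version that does not. Unblinded staff may send reminders or the self-completion link, but do not take answers.
- In 9.2, add telephone as a source of follow-up KOOS-4.
- Require items to be read verbatim, and record the mode of completion for each questionnaire in REDCap.
- Report the primary outcome by mode, or repeat it without phone-collected scores. The detail can sit in the statistical analysis plan, but the mode field must exist from the start of follow-up.

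The cost is a change of REDCap user rights, possibly one edited notification, and one data field. There are two downsides. Callers must be drawn from existing staff who do not handle allocation or SAE data, which limits rostering. The analysis without phone scores also drops some late responders, so it is a check on the main result and not a replacement for it.
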